3.3.1.4 Post-Treatment Period

The subjects will be asked to come back to the CRU at two occasions during the post-treatment period: these visits should occur at Week 9 (Visit 8) and at Week 13 (Visit 9). At Visit 8 and 9, blood sampling will be collected as well as 24-hour urine collection for impurities dosing. Stools samples will be collected only at Visit 8 (week 9) and Visit 9 (Week 13).

3.3.1.5 End-of-Study (EoS)/Early Discontinuation Visit (ED) (Visit 10)

Subjects will be discharged from the study after completion of the EoS visit for follow-up assessments as described in the Schedule of event (see Attachment #1_Section 15.1) which will happen approximately 4 weeks after Visit 9, or earlier in case of early discontinuation.

3.3.2 Subjects Disposition

All subjects visits will be out-patient, except for Visit 2 (Day -1 to Day 2), Visit 7 (Day 35 to Day 36) and Visits 8 and 9 (where subjects will be hospitalized in the CRU). For convenience, subjects may come the evening before the hospitalisation as study assessments start early morning.

3.3.3 Study Duration

For each individual subject, the study is expected to last approximately 5,5 months, including up to 42 days for screening assessments, 35 days of treatment and a 3-month post-treatment follow-up period.

3.4 Study Conduct

It is planned to dose the subjects based on enrolment capabilities of each Clinical Research Units (CRU) and to limit as much as possible the number of cohorts. As there are no safety concerns or limitation with the administration of study drug, multiple subjects may be dosed at the same interval. The recruitment of subjects will be competitive between the CRUs.

3.5 Rationale for the Study Design

Discussion of Design

The primary objective of the study is to investigate the Blood Lead Levels after the chronic oral administration of Smecta® in subjects suffering from chronic functional diarrhoea. In each subject, lead concentrations obtained at several occasions during and after dosing with Smecta® will be compared to each individual baseline data. Other elemental impurities levels will be assessed in blood comparatively to baseline. Moreover, 24h urine level of all these impurities will be collected and assessed by mean of validated analytical methods. Samples of biobanking will be collected for potential other elemental impurities assessments as well as the potential measurement of lead in plasma. Stools samples and the assessment of stool consistency and stool frequency will be also collected for microbiote assessment as ancillary study.

Considering the extensive distribution of lead in the body as well as its long term residence time, a post-treatment follow-up period of 3-months has been considered appropriate to detect any change in the elemental impurities within the frame of a chronic administration of Smecta®.

Dose Selection and Dosing Regimen

The dose of Diosmectite (i.e. 1 sachet (3g) TID) is the recommended dose for Smecta® in the indication of chronic diarrhoea in an adult population.

For the purpose of this study, and in order to potentially limit variability and increase the bioavailability of lead (higher at low pH) dosing of Smecta® will occur in condition of fast 30 minutes before breakfast, 1 hour before noon lunch and 1 hour before evening dinner.

Five (5) weeks can be considered as a repeated chronic administration as chronic diarrhoea is defined as usually lasting more than 4 weeks.

Population Selection and Sample Size

The targeted subject population to assess the primary endpoint are subjects with chronic functional diarrhoea, one of the indication of Smecta® with subjects treated daily for several weeks.

Indeed, lead absorption could be different in subjects with normal gastro-intestinal transit time from patients with various gastrointestinal disorders of organic origin. Moreover patient with acute diarrhoea require a treatment lasting usually for 3 to 7 days that is far from chronic condition

Important factors, that impact the fraction of lead that is absorbed, may depend on the subject's age, gender, smoking, fasting and nutritional status (Falq et al. 2011); this is why the subjects above 60 years of age will not be included in the study. Smoking and nutritional status will be part of the demographic data collected in this study. Smecta intake and fasting status will be standardized as far as possible. To have approximately equal representation in each gender, it is planned to enrol a minimum of 40% of each gender, with gender distributed approximately equally between sites (e.g. no site with less than 35% of one gender).

See Section 8.1.2 for sample size determination.

4 POPULATION RECRUITMENT, ENROLMENT AND WITHDRAWAL

4.1 Definitions

Screened Subject:

A screened subject is a subject who correspond to the preselection criteria, who signed the Informed Consent and could potentially be enrolled into the study.

Screening Failure:

A subject is considered as a screening failure when he/she is not enrolled in the study after signing the Informed Consent.

Subject Enrolment:

A subject is considered as enrolled in the study when he/she is assigned to a treatment.

Subject Drop-out:

A subject will be considered as drop-out when, for any reason, he/she withdraws from the study or is discontinued from the study after enrolment.

4.2 Recruitment of Population

As described in Section 3.3.1, subjects will be screened within 42 days before dosing on a free voluntary basis. The criteria for enrolment must be followed explicitly. If a subject who does not meet enrolment criteria is inadvertently enrolled, he/she should be discontinued from the study and the Sponsor or its designee must be contacted.

As illustrated in the Study Schedule of Events (see Section 15.1), eligibility of subjects in the study will be based on the results of a screening medical history (including any pre-existing conditions, and previous/concomitant medication(s)), physical examination, clinical laboratory tests, vital signs and electrocardiogram (ECG). These tests / assessments may be performed at any time during the screening period (Day -42 to Day -21, included) after

Informed Consent signature. Results of tests and assessments required at screening should be available to confirm subject's eligibility prior to first dosing on Day 1.

4.3 Inclusion Criteria

Potential study subjects may be entered in the study if they meet all of the following criteria:

- (1) Provision of written informed consent prior to any study related procedure.
- (2) Male or female subjects aged between 18 and 60 years (inclusive) at the time of giving informed consent.
- (3) Subjects with chronic functional diarrhoea defined as "Loose (mushy) or watery stools according to Bristol scale grade 6 and 7, occurring in at least 75% of stools for the last 3 months with symptoms onset at least 6 months before diagnosis, without or with pain (including Irritable Bowel Syndrome)" as documented in subject's medical history.
- (4) Body Mass Index (BMI) between 19 and 32 kg/m² (inclusive), with minimum body weight of 50 kg, at screening.

4.4 Exclusion Criteria

Potential study subjects may not be entered into the study if any of the following apply:

Exclusion criteria related to the disease:

- (1) Identified or strongly suspected organic cause to diarrhoea, e.g. ulcerative colitis, Crohn's disease, Celiac disease, bowel malabsorption, chronic pancreatitis, chronic diarrhoea primarily due to diabetes.
- (2) Any drug induced diarrhoea.

Exclusion criteria related to the study drug:

- (3) Prior exposure to diosmectite or other clay(s) or charcoal or other compounds of mineral origin e.g. talc, kaolin, etc. within 1 month prior to screening.
- (4) Except the administration of Smecta® as part of the study treatment, subject should not self-administer any other diosmectite, including Smecta or other clays or charcoal or other compounds of mineral origin during the study..
- (5) History of any serious adverse reaction or adverse event or hypersensitivity to any component of Smecta®.
- (6) Active lactose and/or fructose Intolerance, deficit in sucrose/maltase or glucose malabsorption as documented in subject's medical history.
- (7) Repeated daily intake of drugs with narrow therapeutic index margin (e.g. digoxin, theophylin) (see list in Attachment #4 Section 15.4).

Exclusion criteria related to primary end point:

- (8) Known domestic, leisure or professional exposure to elemental impurities, notably lead, arsenic, cadmium, mercury, aluminium as e.g. building workers, metallurgy, auto repairers, scrap metal recyclers, painting, pottery, shooting (see complete list in Attachment #6_Section 15.6).
- (9) Artificial feeding.
- (10) Subjects eating shellfish (crustaceans, molluscs) more than 2 times a week.
- (11) Subjects living in an old building or house using materials containing lead.
- (12) Planned changes either of residency or of professional/leisure activities during the study (including follow-up period) that may increase the likely exposure to elemental impurities.

Exclusion criteria related to the ancillary study on digestive microbiota:

- (13) Antibiotic agent intake within the month prior to baseline visit (Day -1).
- (14) Risk of antibiotic treatment course during the study.
- (15) Need for metformin and or proton pump inhibitors (PPI) intake within the month prior to baseline or during the study.

Other Exclusion criteria related to the study protocol:

- (16) Receipt of any investigational agent or study drug within 3 months prior to screening.
- (17) Presence of clinically significant physical, laboratory, vital signs, or ECG findings that, in the opinion of the Investigator, Medical Monitor, and/or the Sponsor, may interfere with any aspect of study conduct or interpretation of the results.
- (18) History of any major surgery within 6 months prior to screening or anticipated surgery during the study.
- (19) Women who are breastfeeding or are planning to become pregnant during the study,
- (20) Positive pregnancy test at screening or baseline.
- (21) Loss or donation of blood >500 ml within 3 months before screening, and/or going to donate blood during the study.
- (22) Poor venous access as defined by the Investigator or designee.
- (23) Positive for hepatitis B antigen or hepatitis C virus.
- (24) Positive results for human immunodeficiency virus, or had received diagnosis for acquired immunodeficiency syndrome.
- (25) No history or clinically significant symptoms or severe disease, including cardiac, neurological, pulmonary, hepatic, biliary, gastrointestinal, endocrinologic, or renal disorders, or cancer within the last 5 years (except localised or in situ cancer of the skin and cervical cancer in situ).
- (26) Need for special dietary restrictions, unless the restrictions are approved by the Investigator.
- (27) Likely to be uncompliant or uncooperative during the study, in the judgment of the Investigator.
- (28) Unable to understand the nature, scope and possible consequences of the study, in the judgment of the Investigator.
- (29) Any known factor, condition, or disease that might interfere with treatment compliance or study conduct such as drug or alcohol dependence or psychiatric disease.
- (30) Sponsor employees or Investigator site personnel directly affiliated with this study, and their immediate families. Immediate family is defined as a spouse, parent, child or sibling, whether biological or legally adopted.

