From more than 40 years of sales of Smecta®, no adverse events potentially related to elemental impurities, particularly saturnism and/or chronic lead intoxication symptoms have been reported to Ipsen or to Health Authorities. In addition, no signal within the Ipsen Pharmacovigilance Safety Data Base, and notably in targeted body systems (such as nervous system, blood and lymphatic, renal and urinary), has been detected.

Furthermore, declaration of lead intoxication is mandatory in France. Between 1995 and 2014, neither lead intoxication, nor blood lead level $> 100 \mu g/l$ have been reported in children taking Smecta® to the SNSPE (Système National de Surveillance de Plombémie chez l'Enfant).

However, regarding the new ICHQ3D guidelines, Smecta® does not comply with the new requirements. Therefore, the MAH considered that in order to perform an appropriate risk assessment of elemental impurities contained in Smecta®, including lead as primary elemental constituent, clinical data need to be generated in humans after chronic administration of Smecta®.

Lead is a common element found in low concentration in the Earth's crust. It is widely used in industry, particularly in products such as construction materials, paint, batteries and piping. Lead causes health problems such as toxicity of the liver, kidneys, hematopoietic system and nervous system. During the 70's and 80's, concern over lead related health problems led to the introduction of unleaded gasoline and the banning of lead based paint (for review see Kim et al. 2015). After lead enters the body, it can transit along several pathways depending on its source (organic or inorganic). The fraction of lead that is absorbed depend mainly on the physical and chemical form. Other important factors are subject's specific such as age, gender, smoking and nutritional status. The half-life of lead in the blood compartment is about 40 days in adults (99% of circulating lead is contained in the erythrocytes, Rabinowitz, 1991). The half-life of lead in blood of children and in pregnant women is reported to be longer due to bone remodelling. Residence time in other organs such as bone is much longer and ranges from 10 to 30 years. Whole blood and serum/plasma have been used as biological fluid used for the assessment of lead exposure both for screening, bio-monitoring and diagnostic purposes (Barbosa F et al. 2005, Falq et al. 2011).

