3.3.1.1 Screening Period

The subjects will attend the CRU (Visit 1) to enter the screening period within 21 to 42 days prior to dosing Visit 2.

After a subject has been checked for pre selection criteria, has received complete explanations and response(s) to his/her potential questions about the study by the Investigator (or designee) and has been given reasonable time to think about it, a signed and dated informed consent form will be obtained prior to any study procedures.

Once informed consent is obtained, subjects will be allocated a study-specific subject number which must comply with formatting specifications provided by the Sponsor.

Demographic data will be collected including race, smoking status, alcohol consumption, and dietary habits.

The screening tests and assessments will then be performed to check compliance with Inclusion/Exclusion criteria and study restrictions. The results must be obtained and confirm subject's eligibility prior to dosing on Visit 2 at Day 1.

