6.2 Concomitant Therapy(ies)

Any other treatment should be taken at least 2 hours before or after the ingestion of Smecta®.

Drugs with a low therapeutic index are specifically excluded (e.g. digoxin, theophylline) if repeated daily intake is needed.

Antibiotics are forbidden during the study as they could interfere with microbiote evaluation.

Compounds containing Diosmectite or similar compounds or mine extracts, as well as other compounds containing elemental impurities such as antacids (e.g. Maalox) are excluded.

The list of excluded concomitant medications are listed in Attachment #4 Section 15.4.

During the study the Investigator should check if the subject has received any concomitant medication/therapy that is not permitted at study entry.

Subjects will provide information about all previous medication taken over the last month and investigational drug taken over the last 3 months, and medication taken during the study, and this information will be recorded on the appropriate eCRF.

Contraception

No specific contraception methods are required for the study participation. A pregnancy test will be performed on screening, baseline and end-of-study visit. Women are requested to be non pregnant at inclusion and not becoming pregnant during the treatment phase of the study.

Rescue Medication

Loperamide will be allowed as rescue medication should the chronic diarrhoea worsen during the study.

The recommended dose regimen will follow the SmPC of loperamide with a maximum daily dose not exceeding 12 mg.

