3.2.2 Biological and clinical evaluations

3.2.2.1 Biological evaluations

Biological evaluations concern blood samples for elemental impurities, urine collection (24-hour) for elemental impurities.

The baseline for blood concentrations (lead and other elemental impurities) will be the average between the available screening and pre-dose (Day-1) values (as defined in [Appendix 1 \(5\)](#)).

For blood lead concentrations, absolute values and changes (as defined in [Appendix 1 \(6\)](#)) from BLL baseline will be summarized for all post-baseline time-points on the ITT and the PP population.

Additionally, for all follow-up time points, absolute changes from D36 (in the morning) will be calculated and summarized.

Corresponding listings will be provided on ITT population.

Plots of mean absolute changes over time (with 95% confidence interval) will be provided on ITT and PP population and individual corresponding plots on ITT population (one graph for full profile). For blood lead concentrations, same analyses by country will be presented.

For other elemental impurities blood concentrations, the analysis will also be described in the same way as for blood lead concentrations expect for plots of means and individual corresponding plots which will be provided only for arsenic and barium parameters.

The baseline for urine concentrations (lead and other elemental impurities) and Ae parameter will be defined as the last available (and reliable if applicable) assessment collected prior to receiving dose of Smecta® on Day 1.

For urine lead concentrations and other elemental impurities, the same approach for blood lead concentrations will be done expect that there will be no plots.

The cumulative amount of EI (Elemental Impurities) excreted in urine (the Ae parameter) will be calculated (as defined in [Appendix 1 \(7\)](#)) and summarized at each scheduled assessment with absolute changes from baseline and absolute changes from D36 (in the morning) and listed on ITT population. Plot of mean of this cumulative amount (with 95% confidence interval) will be provided on ITT population if the number of data above the limit of quantification is sufficient.

The volume of urine will be only listed on ITT population.

For summary statistics, the following will be presented: n, arithmetic mean with its 95% confidence interval, standard deviation (SD), median and the range (minimum, maximum).

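### The one-month clay-free period before screening is shorter than the stated 40-day blood-lead half-life, so earlier clay use can lower the measured change from baseline by an amount the plan does not measure

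*Protocol*

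**What the plan says.** - **Clay before the study.** Protocol 4.4, criterion 3, excludes "Prior exposure to diosmectite or other clay(s) or charcoal or other compounds of mineral origin e.g. talc, kaolin, etc. within 1 month prior to screening". Criterion 4 adds that the "subject should not self-administer any other diosmectite, including Smecta or other clays or charcoal or other compounds of mineral origin during the study". Criterion 16 separately excludes receipt of an investigational agent or study drug in the 3 months before screening.
- **Lead kinetics.** Protocol 1.7: "The half-life of lead in the blood compartment is about 40 days in adults". For slower pools: "Residence time in other organs such as bone is much longer and ranges from 10 to 30 years".
- **Timing.** Protocol 3.3.1.1: "The subjects will attend the CRU (Visit 1) to enter the screening period within 21 to 42 days prior to dosing Visit 2". Treatment runs from Day 1 to Day 35, with a morning sample on Day 36 and follow-up to Day 125.
- **Baseline.** SAP 3.2.2.1: the blood baseline "will be the average between the available screening and pre-dose (Day-1) values". The primary endpoint is the absolute change in BLL from that baseline. The study is open-label and non-comparative.
- **History taken.** Protocol 6.2: "Subjects will provide information about all previous medication taken over the last month". SAP 1.3.2.4 and 3.2.11 add an item on prior medications for chronic diarrhoea, with no look-back period stated.

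Neither document discusses carry-over from earlier clay use or a drifting baseline.

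**The concern.** The clay-free window ends at screening and is shorter than one half-life of the quantity being measured. A subject whose BLL was raised by an earlier course would give two baseline samples on a falling curve. Averaging screening with Day -1 puts the older, higher value into the reference. The same decay continues through treatment and follow-up and is counted as part of the Smecta effect, because each subject is compared only with their own baseline.

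The error runs one way, towards a smaller apparent rise, in a study meant to find out whether lead is absorbed. Such subjects are foreseeable. Chronic functional diarrhoea is a marketed indication (Protocol 1.1), the population is described as needing repeated chronic administration (1.5), and 5 weeks is taken as the likely minimum length of a repeated course (1.4). Attachment 4 itself lists the clay exclusion as one that protects the primary endpoint. Section 3.5 uses lead's long residence time to justify three months of follow-up, but the same reasoning is not applied to the period before treatment.

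**Working it through.** The plan gives no carry-over figure to reproduce, so the check starts from its inputs.

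**Inputs from the documents:** half-life 40 days (Protocol 1.7); last clay use 30 days before screening, the limit of criterion 3; screening 21 or 42 days before Day 1 (3.3.1.1); 35 days of dosing; baseline = mean of screening and Day -1 (SAP 3.2.2.1).

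**Assumptions:** one compartment with first-order decay (bone ignored); the same daily lead intake and absorption before and during the trial, so that absorption cancels.

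**Clay-free time before Day 1:** 30 + 21 = 51 days to 30 + 42 = 72 days, or 1.3 to 1.8 half-lives.

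**Fraction of the earlier excess remaining, 2^(-t/40):**

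| Time point | Screening 21 days before Day 1 | Screening 42 days before Day 1 |
|---|---|---|
| Screening | 2^(-30/40) = 0.595 | 0.595 |
| Day -1 | 2^(-50/40) = 0.420 | 2^(-71/40) = 0.292 |
| Averaged baseline | 0.508 | 0.443 |
| Day 36 | 2^(-86/40) = 0.225 | 2^(-107/40) = 0.157 |
| Fall, baseline to Day 36 | 0.282 | 0.287 |

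**True five-week rise** as a fraction of the steady-state excess: 1 - 2^(-35/40) = 0.455.

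**Hidden share of that rise** = fall x earlier excess / five-week rise:

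- Long-term user (earlier excess = 1): 0.282/0.455 to 0.287/0.455 = 62-63%.
- One earlier 5-week course (earlier excess = 0.455): 28-29%.
- One week of use (1 - 2^(-7/40) = 0.114): 0.114 x 0.282/0.455 = 7%.

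**Sensitivity, long-term user:**

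- Half-life of 30 days: 47-49%. Half-life of 50 days: 72-75%.
- Day -1 alone as baseline: (0.420 - 0.225)/0.455 = 43% and (0.292 - 0.157)/0.455 = 30%. Averaging in the screening value therefore enlarges the bias.
- If criterion 16 is read as a 90-day Smecta washout: 22% (10% after one course).

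**Day 125.** The true remaining rise is 0.455 x 2^(-89/40) = +0.10 of the steady-state excess. Carry-over contributes -0.41 to -0.46 after long-term use, or -0.19 to -0.21 after one 5-week course. Either way, a subject at the limit would appear to fall below baseline.

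**Cohort mean** = share of such subjects x hidden share (28% for one course, 62% for long-term use). The share is not in the documents, so it is shown as a range:

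| Share at the limit | One course | Long-term | A true mean rise of 18.6 µg/l would read |
|---|---|---|---|
| 10% | 3% | 6% | 18.1 to 17.4 |
| 25% | 7% | 15% | 17.3 to 15.7 |
| 50% | 14% | 31% | 16.0 to 12.8 |

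The 18.6 µg/l is the plan's own margin (50 - 31.4), used here only for scale.

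**The case against.** - **The larger figures are limit cases.** About 62% needs a subject at steady state who stopped exactly 30 days before screening with trial-level lead exposure. The trial batch is chosen for maximal lead (Protocol 5.1.1), and fasting dosing is meant to raise lead bioavailability (3.5). Ordinary earlier use would probably leave a smaller excess, and the hidden share falls in proportion. If last use were spread evenly over 30 to 180 days before screening (an assumption), the average hidden share is 0.356 of the limit value: about 22% for long-term use and 10% for one course. This stands.
- **Such subjects may be few.** Inclusion criterion 3 requires loose stools in at least 75% of stools over three months, and Protocol 1.6 expects Smecta to improve symptoms. Someone well controlled on clay until a month before screening may not qualify. This lowers the likely share without bounding it.
- **Criterion 16 may already impose three months.** Section 5.1 calls Smecta the study drug. However, 6.2 pairs one month for medication with three months for investigational drugs, criterion 3 is the more specific rule, and criterion 16 does not cover other clays. The two need reconciling.
- **Recent users might seem impossible to identify afterwards.** A reader could infer this from the one-month history in 6.2, but the SAP's chronic-diarrhoea medication item has no stated limit and could capture them. The supportable statement is that the plan does not ensure they are captured.
- **Existing safeguards.** Screening and Day -1 BLL are reviewed on an ongoing basis (Protocol 8.2) and individual profiles are plotted. The optional sensitivity analysis in SAP 3.2.2.1 excludes subjects with a high baseline lead level. None of these selects on earlier clay use or examines the direction of the baseline.

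**Conclusion.** The point holds as a one-directional risk to the change-from-baseline endpoint. It should be fixed, and confidence is medium. For a subject who stopped clay at the limit of criterion 3, the decay hides about 28% of the five-week rise after one earlier 5-week course and up to about 62% after long-term use. It hides less if use was brief, ended earlier or gave lower lead exposure. These figures rest on a single 40-day compartment and equal lead intake. They describe diosmectite, because the documents give no lead content for other clays.

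Two stronger readings are not supported. One is that the trial's mean result hides most of the lead rise: the documents do not give the share of recent users, and at 10% the understatement is about 3-6%. The other is that every lead conclusion is biased towards safety. The SAP also summarises absolute BLL at each time point, and carry-over raises those values, so a comparison with 50 µg/l is not made falsely reassuring.

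**What to change.** 1. **Eligibility text.** Reconcile the clay-free period in criterion 3 with the half-life in Protocol 1.7 and with the 3-month wording of criterion 16, and state which criterion governs Smecta. The length is for the sponsor to set and justify.
2. **History.** In Protocol 6.2, lengthen the look-back for clays, charcoal and mineral antacids to several of the stated half-lives. For scale, four half-lives are 160 days and leave 2^(-4) = 6% of an excess. Record product, duration and date of last use, and use the existing chronic-diarrhoea medication item to do so. For subjects already enrolled, collect this retrospectively.
3. **Analysis.** In SAP 3.2.2.1, tabulate the BLL change from screening to Day -1 as untreated drift. Repeat the primary BLL summary (a) without recent clay users, with the cut-off fixed before the data are reviewed, and (b) with Day -1 alone as baseline.

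The cost is a text amendment, one added eCRF question and a few tables from samples already planned. Summary (a) will have fewer subjects and wider intervals. Summary (b) reduces the bias without removing it, and rests on one baseline sample instead of two.

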On pre-dose before dosing (morning, approximately 7am on Day 2, and on pre-dose of any of the dosing occasion on the other days)

b On pre-dose before dosing (mcc Body height only at screening.

- Pregnancy test: serum at screening and urine at baseline and EoS.
 - Time window for PK sampling: $\pm 15 \text{ min}$ To be performed 24h before the visit 3
- l sample to be taken at screening visit at the CRU and 1 sample by the subject at home at Day-14 ±1 day
- Smecta® should be taken fasting and at least one hour before meal, except for breakfast at least 30 minutes before.
- C-reactive protein to be analysed only at screening м т. т. т. ж
- Diary to be completed at screening retrospectively to cover the past 24h, and 24h before the Day-14 stool sample To the extent possible, to collect the data over approximately 24h preceding the stool sample taken at the visit 24h (i.e. 1 day or more).

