- g 1 sample to be taken at screening visit at the CRU and 1 sample by the subject at home at Day-14 ± 1 day
- h Smecta® should be taken fasting and at least one hour before meal, except for breakfast at least 30 minutes before.
- i C-reactive protein to be analysed only at screening
- j Diary to be completed at screening retrospectively to cover the past 24h, and 24h before the Day-14 stool sample
- k To the extent possible, to collect the data over approximately 24h preceding the stool sample taken at the visit 24h (i.e. 1 day or more).

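### The one-month antibiotic, PPI and metformin windows protect only the Day -1 microbiota sample; the screening and Day -14 stool samples can follow permitted use by less than a month

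*Protocol*

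**What the plan says.** Protocol 4.4 lists criteria 13 to 15 under a heading that ties them to the ancillary microbiota study:

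- Criterion 13: "Antibiotic agent intake within the month prior to baseline visit (Day -1".
- Criterion 14: "Risk of antibiotic treatment course during the study".
- Criterion 15: "Need for metformin and or proton pump inhibitors (PPI) intake within the month prior to baseline or during the study".

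Protocol 6.2 adds a general prohibition and its reason: "Antibiotics are forbidden during the study as they could interfere with microbiote evaluation". Attachment 4 lists the same three drug groups as excluded previous and concomitant medication but gives no time window.

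Stool sampling starts before the point from which criteria 13 and 15 count back. Protocol 4.2 sets the "screening period (Day -42 to Day -21, included". The stool footnote to the schedule in Attachment 1 asks for one "sample to be taken at screening visit at the CRU and 1 sample by the subject at home at Day-14 ±1 day", and SAP 1.3.3 repeats it. A third pre-dose sample is taken at the Day -1 visit (Protocol 3.3.1.2 and Attachment 1).

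Protocol 3.2.2.1 compares microbiota during treatment and follow-up with baseline, without saying which pre-dose sample or samples form that baseline. SAP 1.1.3 and 3.1.4 leave the microbiota analysis to a separate plan.

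**The concern.** The three criteria exist to keep recent drug exposure from disturbing the microbiota results, and three pre-dose samples are collected. A month counted back from the last of them gives the first two no such assurance. The prohibition during the study does not fill the gap: even if it starts at the screening visit, it cannot reach use that ended before screening, and criterion 14 looks only forward.

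The study has a single arm, so no control group could separate a flora still recovering from a drug from a change caused by Smecta. If the screening and Day -14 samples contributed to the baseline, such recovery could appear as a change on treatment. If they were used to describe spontaneous variation before treatment, it could inflate that variation. Protocol 7.5 makes analysis of the follow-up stool samples depend on a significant change during treatment, so a disturbed baseline could also affect that step.

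**Working it through.** No figure in the plan bears on this point, so the check is a day count.

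**Inputs**
- Window: one month back from Day -1 (Protocol 4.4). The month is not defined; 30 days is the main assumption, with 28 and 31 as alternatives.
- Screening day S: Day -42 to Day -21, which is 22 possible days (Protocol 4.2).
- Stool samples: S, Day -14 (±1 day) and Day -1 (Attachment 1).

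**Last permitted antibiotic day.** Day -31 is exactly 30 days before Day -1 and is counted as inside the window, so the window alone permits use up to Day -32. The reading kinder to the protocol also starts the prohibition in 6.2 at the screening visit. Then L = the earlier of Day -32 and S - 1, and each gap is the sample day minus L:

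| S | L | Gap to screening sample | Gap to Day -14 | Gap to Day -1 |
|---|---|---|---|---|
| -42 | -43 | 1 | 29 | 42 |
| -32 | -33 | 1 | 19 | 32 |
| -31 | -32 | 1 | 18 | 31 |
| -21 | -32 | 11 | 18 | 31 |

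Example for S = -21: -21 - (-32) = 11; -14 - (-32) = 18; -1 - (-32) = 31. The ±1 day on the home sample moves 18 to 17 or 19, and 29 to 28 or 30.

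**Less kind reading.** If the prohibition does not apply between screening and the start of the window, L = Day -32 throughout. The Day -14 gap is then 18 days for every S, and a subject screened before Day -32 could take an antibiotic after the screening sample and still satisfy criterion 13.

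**Sensitivity**
- With a 30- or 31-day month, both early samples (home sample at nominal Day -14) can lie within a month of permitted use on all 22 screening days, under either reading.
- With a 28-day month this holds on 22 of 22 days under the less kind reading and 21 of 22 under the kinder one. The exception is screening on Day -42, where the Day -14 gap is 29 days.
- If Day -31 itself is permitted, the gaps for S = -21 fall by one day: -21 - (-31) = 10, -14 - (-31) = 17 and -1 - (-31) = 30.

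**PPIs and metformin.** Criterion 15 also excludes a need during the study, so the exposure left open is use that ended before screening. The kinder reading's day count then applies.

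**After the change.** With a 30-day month counted back from the screening sample, the last permitted day is -42 - 31 = Day -73 (S = -42) to -21 - 31 = Day -52 (S = -21). The smallest gaps, with no use after screening, become 31 days to the screening sample, -14 - (-52) = 38 to Day -14 and -1 - (-52) = 51 to Day -1.

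**The case against.** The best defence is that the protocol names its anchor, calls Day -1 the baseline, compares microbiota with baseline and gives the Day -1 sample its full month. Protecting the named comparator is a coherent choice. That stands, and it confines the point to the two earlier samples.

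Four stronger readings are tempting but not supported:

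- **That the early samples fall in a month the protocol failed to keep clear.** The month before Day -1 is kept clear by criterion 13. The gap concerns use before that month. That a clear month was meant for every pre-dose sample is an inference from the heading over criteria 13 to 15 and the reason given in 6.2; it is not stated.
- **That a false Smecta effect will result.** No passage says what the screening and Day -14 samples are for, and the separate microbiota plan is not available. It may already deal with recent exposure.
- **That the stool-diary results are compromised.** SAP 3.2.2.2 takes the last available pre-dose assessment as the diary baseline, so the earlier diaries enter change from baseline only if the Day -1 value is missing.
- **That the anchor contradicts criterion 3.** Criterion 3 bars mineral products "within 1 month prior to screening", and the blood lead baseline averages the screening and Day -1 values, so that endpoint needs a screening anchor. Different endpoints can have different anchors.

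**Conclusion.** The point holds as a limited mismatch between eligibility windows and sampling schedule. By the protocol's own one-month standard, only one of the three pre-dose microbiota samples is guaranteed clear. The minimum gaps of 1 to 11 days and 18 to 29 days for the other two rest on a 30-day month and on antibiotics being barred from the screening visit on; they are what the criteria permit. The documents do not show how many subjects would have such exposure.

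The consequence is conditional on the screening or Day -14 sample being used in the baseline or to describe variability. The endpoint is exploratory, and the primary blood lead analysis and the safety analyses are untouched. This is a worthwhile, inexpensive improvement and no more.

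**What to change.** Reconcile criteria 13 and 15 with the stool schedule by adding the same one-month window before the screening sample and keeping the existing one, so that the period runs unbroken from one month before that sample to Day -1. Do not simply exchange the baseline anchor for a screening anchor. Criterion 13 would then no longer cover the interval from screening to Day -1: antibiotic use on Day -20 in a subject screened on Day -42 is caught by it now and would not be afterwards.

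For subjects already enrolled, the separate microbiota plan should name the sample or samples that form the baseline, and leave out any pre-dose sample taken less than one month after recorded antibiotic, PPI or metformin use. This should need no new data: Protocol 6.2 already collects medication over the last month, and Attachment 1 places prior medication at screening and concomitant medication at every visit.

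The cost is two amended criteria and probably a few more screen failures, or a short addition to the microbiota plan and a few omitted exploratory samples. The documents give no basis for a firmer count.
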